## **DATA ANALYSIS:**

### **Sample Size Considerations**

A sample size of n=20 Duobrii-treated subjects allows 80% power at 5% significance to detect a minimum reduction of 35% in the median number of lesions at week 12 with the one-sided Wilcoxon nonparametric test. This calculation assumes an average count of 15 AKN lesions at baseline and a standard deviation of 7 lesions around the mean difference at week 12, and a drop-out rate of 30%. These numbers are based on data reported by Okoye et al. (2014), who compared lesion counts at week 16 to baseline in a set of 11 UVB-treated subjects. The sample size calculation is based on the asymptotic relative efficiency of the Wilcoxon test compared to paired Student's t-test. A sample size of n=20 treated subjects compared to n=10 placebo-treated ones allows 80% power at 5% significance to detect a minimum 50% difference between proportions of patients with a reduced number of AKN lesions. This calculation is based on the application of a one-sided Z-test for the difference between two independent proportions and also assumes a maximum 30% dropout rate within each arm.

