## **Primary Endpoint**

The primary analysis for the primary endpoint will test for a reduction in lesion counts after 12 weeks of treatment. We will apply the two-sided Wilcoxon test to assess the significance of the difference between pre- and post-treatment median numbers of lesion counts. The secondary analysis will compare the reduction in lesion counts between active and placebo groups after 12 weeks. For this purpose, we will apply the Z-test to verify the hypothesis that the proportions of patients with reduced AKN lesions differ between active and placebo groups. A more comprehensive analysis will adjust a generalized linear mixed-effects model, based on Poisson distribution, including time and treatment group as fixed factors and a random intercept for each subject. This model will include the whole time-course and contrasts of interests will be estimated.

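### The active arm is sized on a one-sided Wilcoxon test but the primary analysis is two-sided; at the planned 30% dropout, two-sided 5% power for a 35% reduction is about 71%, not 80%

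*Combined protocol and SAP*

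**What the plan says.** Under Data Analysis, Sample Size Considerations states: "A sample size of n=20 Duobrii-treated subjects allows 80% power at 5% significance". The target is a 35% reduction "in the median number of lesions at week 12 with the one-sided Wilcoxon nonparametric test". The inputs are an "average count of 15 AKN lesions at baseline and a standard deviation of 7 lesions around the mean difference at week 12", with 30% dropout. The stated method scales a paired t-test by the asymptotic relative efficiency (ARE) of the Wilcoxon test.

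The Primary Endpoint paragraph in the same part of the document describes the primary analysis as follows: "We will apply the two-sided Wilcoxon test to assess the significance of the difference between pre- and post-treatment median numbers of lesion counts". It gives no significance level of its own.

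For the comparison between arms, Sample Size Considerations says: "This calculation is based on the application of a one-sided Z-test for the difference between two independent proportions". The Primary Endpoint paragraph says only that the Z-test will examine whether "the proportions of patients with reduced AKN lesions differ between active and placebo groups". It does not state sidedness, and neither section gives the assumed proportions.

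**The concern.** A power statement holds only for the test it was computed for. Here the sizing and the primary analysis concern the same comparison, baseline against week 12 in treated subjects, but the sizing puts the whole 5% in one tail and the analysis splits it over two. Both statements are current text, and the amendment lists touch neither.

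The 80% figure is the stated justification for the size of the active arm. If the planned test has less power than claimed, a non-significant result says less about the absence of a 35% reduction than a reader would infer from the protocol. The matter concerns power only: a two-sided test at 5% keeps its type I error.

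**Working it through.** **Inputs from Sample Size Considerations**

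- Reduction to detect: 0.35 × 15 = 5.25 lesions
- SD of the paired difference: 7 lesions, so d = 5.25 / 7 = 0.75
- Completers: 20 × (1 − 0.30) = 14
- Significance level: 5%

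**Assumptions, because the plan gives no value**

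- ARE = 3/π = 0.955, the value under normal differences; range shown 0.864 to 1.
- The 5% level also applies to the two-sided test.

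**Formula.** With n* = ARE × completers, degrees of freedom n* − 1 and noncentrality λ = d√n*, power is the probability that a noncentral t exceeds the upper critical value at 0.05 (one-sided) or 0.025 (two-sided).

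**Step 1: reproduce the plan's figure (one-sided).** The paired t-test needs n = 12.46 for 80% power. Dividing by the ARE gives 12.46 / 0.955 = 13.05, so 14 completers, and 14 / 0.70 = 20 enrolled. This is the plan's n=20. With 14 completers, n* = 13.37, λ = 0.75 × √13.37 = 2.74, the critical value is 1.778, and power is 82.7%. Thirteen completers fall just short of 80%.

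**Step 2: the same design, two-sided.** n* and λ are unchanged and the critical value rises to 2.172. Power is 71.4%, so the chance of missing the effect is 1 − 0.714 = 0.286, about 29%.

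| ARE | One-sided 5%, 14 completers | Two-sided 5%, 14 completers | Two-sided 5%, all 20 complete |
|---|---|---|---|
| 0.864 | 78.8% | 66.2% | 83.4% |
| 0.955 | 82.7% | 71.4% | 87.3% |
| 1 | 84.4% | 73.7% | 88.9% |

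**Step 3: check without the ARE.** A simulated exact signed-rank test on normal differences with 14 completers gives about 82% one-sided and 72% two-sided.

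**Step 4: what 14 completers can detect two-sided with 80% power.** At ARE 0.955, d = 0.833, and 0.833 × 7 = 5.83 lesions, which is 5.83 / 15 = 38.9%. The range is 37.8% (ARE 1) to 41.3% (ARE 0.864).

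**Step 5: what 80% power at a 35% reduction would need two-sided.** The paired t-test needs n = 15.98. Dividing by 0.955 gives 16.73, so 17 completers (80.7%; 16 give 77.9%). Then 17 / 0.70 = 24.3, so 25 enrolled in the active arm (23 at ARE 1, 28 at ARE 0.864).

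**Step 6: the Z-test.** At 30% dropout the comparison is 14 against 7. For a 50-point difference, with the placebo proportion assumed anywhere from 5% to 45%:

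| | Unpooled variance | Pooled variance |
|---|---|---|
| One-sided 5% | 79% to 94% | 73% to 83% |
| Two-sided 5% | 69% to 89% | 60% to 74% |

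The spread shows that no single power figure can be confirmed until the proportions, the variance form and the sidedness are stated.

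**The case against.** **The arithmetic in the sample size section is right.** This stands. For the one-sided test it names, n=20 is correct. The defect is that the analysis section names a different test.

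**The analysis section is itself partly directional.** Its opening sentence speaks of testing for a reduction, so the word two-sided might be the slip. But that sentence is loose, while the sidedness of the test is stated outright. If the sponsor does intend a one-sided test, the analysis text has to change instead; the two sections cannot both stand.

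**A two-sided 10% level would restore the one-sided power.** True, but the only level stated is 5%.

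**The shortfall depends on dropout.** This also stands as a condition. At ARE 3/π, two-sided power passes 80% once 17 of the 20 are evaluable. The Schedule of Events includes a lesion count at early termination, so some dropouts may have a post-treatment count, although the plan does not say whether it enters the week 12 test. The 80% claim, however, is made under the plan's own 30% allowance.

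**A simpler formula gives n=20 two-sided.** A normal approximation with neither the t correction nor the ARE needs ((1.960 + 0.842) × 7 / 5.25)² = 13.95, so 14 completers and 20 enrolled. That is not the method described, and it overstates power at this size: the simulated exact two-sided test gives 72%.

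**Heavier tails would help the Wilcoxon test.** With logistic differences (ARE π²/9 = 1.10) two-sided power is about 78%; with Laplace differences (ARE 1.5) it is about 90%. The plan assumes neither, and neither reproduces n=20 one-sided: 12.46 / 1.10 and 12.46 / 1.5 round up to 12 and 9 completers, or 18 and 13 enrolled.

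**For the Z-test**, saying that proportions differ does not contradict a one-sided test. That part is an omission rather than a contradiction.

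**Conclusion.** The concern holds. The claimed 80% belongs to a one-sided 5% Wilcoxon test, whereas the primary analysis is a two-sided one. For the two-sided test at 5%, with 14 completers and ARE 3/π, power for a 35% reduction is about 71%, roughly 9 points below the claim. Equivalently, 80% power is reached only at a reduction of about 39%. Over ARE 0.864 to 1 the power stays below 80%. The conclusion depends on the 5% level carrying over to the two-sided test and on the planned dropout occurring in full. The primary test remains valid; what is wrong is the power stated for it. The Z-test point is secondary and supports no power figure either way.

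**What to change.** Rewrite the Wilcoxon statement in Sample Size Considerations for the two-sided 5% test named in the analysis section. With 20 enrolled and 14 completers, state either about 71% power for a 35% reduction or 80% power for a reduction of about 39%. Give the ARE value used, and state the significance level in the Primary Endpoint paragraph.

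For the Z-test, make the sidedness explicit and the same in both sections, state the assumed proportions in each arm, and recompute the power for the test chosen. No Z-test power should be written in before those proportions are given.

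The cost is protocol wording and a less favourable Wilcoxon figure; enrolment stays as it is. Keeping 80% power at a 35% reduction with a two-sided test would instead take 25 active subjects. At 2:1 that means 25 / 2 = 12.5, so 13 placebo subjects, or 38 in all against the present 30. Restating the figure is the cheaper repair.

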## **Primary Endpoint**

The primary analysis for the primary endpoint will test for a reduction in lesion counts after 12 weeks of treatment. We will apply the two-sided Wilcoxon test to assess the significance of the difference between pre- and post-treatment median numbers of lesion counts. The secondary analysis will compare the reduction in lesion counts between active and placebo groups after 12 weeks. For this purpose, we will apply the Z-test to verify the hypothesis that the proportions of patients with reduced AKN lesions differ between active and placebo groups. A more comprehensive analysis will adjust a generalized linear mixed-effects model, based on Poisson distribution, including time and treatment group as fixed factors and a random intercept for each subject. This model will include the whole time-course and contrasts of interests will be estimated.

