## **HYPOTHESIS:**

### **Primary Hypothesis:**

1. Subjects treated with Duobrii will experience significant clinical improvement in lesion counts, symptoms associated with AKN as well as minimal dyspigmentation when compared to patients receiving placebo.

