## **STUDY OBJECTIVE**

Evaluate the efficacy and safety of Duobrii in the management of early to mild AKN

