## **ENDPOINTS:**

### **Primary Endpoint**

- The primary endpoint will be clinical improvement as assessed by lesion counts and captured by photography.

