## **STUDY DESIGN OVERVIEW:**

Following IRB approval, we will conduct a single center, prospective, double-blinded placebo vs. active-control trial assessing the efficacy of the vehicle vs. Duobrii, respectively, in the management of AKN over 3 months.

Blinding will be performed by pharmacy and research staff. In addition, different investigators will do the clinical enrollment and follow up vs. statistical analysis.

Patients with class I and class II AKN (Appendix C) from our various clinics at our Skin of Color Center will be screened with plan to enroll 30 participants after obtaining written informed consent. In addition, flyer announcement of our trial will be distributed and active patient recruitment will be conducted at various local barber shops and social media platforms (instagram, twitter and facebook) to increase patient recruitment.

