## **RANDOMIZATION:**

Once a subject meets all the inclusion and exclusion criteria, they will be assigned a randomization number on day 0/baseline. Enrolled subjects will be randomized in a 2:1 ratio of Duobrii to placebo.

The randomization will be performed by designated research staff/personnel at the Icahn School of Medicine using a randomization generator. The subjects and assessors (sub-investigators) will remain blinded to individual treatment assignment during the study. Research staff will also be responsible for blinding of the medication.

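### The analysis labelled primary is a before-and-after test; the Duobrii-versus-placebo test is ranked secondary, so a significant primary result does not test the primary hypothesis

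*Combined protocol and SAP*

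**What the plan says.** All references are to the combined protocol and SAP.

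- **Hypothesis and design.** Primary Hypothesis expects better lesion counts and symptoms, and "minimal dyspigmentation when compared to patients receiving placebo". Study Design Overview describes a "double-blinded placebo vs. active-control trial assessing the efficacy of the vehicle vs. Duobrii". Randomization states: "Enrolled subjects will be randomized in a 2:1 ratio of Duobrii to placebo". The Study Objective and the endpoint definition name no comparator, so the mismatch rests on these three sections.
- **Primary analysis.** Data Analysis, Primary Endpoint: "We will apply the two-sided Wilcoxon test to assess the significance of the difference between pre- and post-treatment median numbers of lesion counts". The arm is not named there. Sample Size Considerations bases the matching calculation on 20 Duobrii-treated subjects.
- **Between-arm analysis.** The same section continues: "The secondary analysis will compare the reduction in lesion counts between active and placebo groups after 12 weeks". The method is a Z-test on the proportions of patients whose count fell. Sample Size Considerations gives it a power statement for a 50% difference in proportions.
- **Count mixed model.** A Poisson model "including time and treatment group as fixed factors and a random intercept for each subject". Contrasts are promised but none is named. Under Secondary Endpoints, the models for the other outcomes do include the time-by-treatment interaction.

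**The concern.** A within-arm test asks whether counts fell. The hypothesis asks whether they fell more on Duobrii than on vehicle. A fall within the Duobrii arm also contains any vehicle effect, the natural course of the disease, regression to the mean, and the effect of the gentle hair care recommended to participants. The placebo arm is there to separate these from a drug effect, and the primary test does not use it.

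The supporting analyses only partly fill the gap. The Z-test counts a fall of one lesion the same as clearance. The mixed model, read as written, has a group difference that is constant over visits, baseline included, so it does not estimate a between-arm difference in change.

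**Working it through.** **Inputs from Sample Size Considerations.** Baseline mean 15 lesions; SD of change 7; 35% reduction, so 0.35 × 15 = 5.25 lesions; dropout 30%, so 20 × 0.7 = 14 Duobrii and 10 × 0.7 = 7 placebo completers.

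**1. The plan's own n.** Standardised change = 5.25/7 = 0.75. A one-sided 5% paired t-test with 80% power needs 13 completers. With the Wilcoxon relative efficiency 3/π = 0.955 it needs 14 (power 82.7%), and 14/0.7 = 20. The stated 20 reproduces, but as a one-sample calculation that uses no placebo data.

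**2. The primary test when the drug adds nothing.** Assume both arms fall by the same fraction r (r is not in the documents). Changes are normal with mean 15r and SD 7; exact two-sided signed-rank test at 5%; 200,000 simulated trials per cell.

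| Equal fall in both arms | 14 Duobrii completers | 20 Duobrii completers |
|---|---|---|
| 10% | 11% | 14% |
| 20% | 31% | 42% |
| 30% | 59% | 76% |

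In a separate simulation with 14 vs 7 completers and equal falls, a between-arm rank-sum test was significant in about 4-5% of trials.

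**3. The count model without the interaction.** The main-effects Poisson model was fitted to expected counts at weeks 0, 4, 8 and 12, 20 vs 10, with a true week-12 ratio of 0.65 (35% advantage). If the advantage grows log-linearly from none at baseline, the single group ratio is 0.817, an apparent advantage of about 18%. If it is fully present from week 4, the ratio is 0.737, about 26%. Both time courses are assumed.

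**4. Power of a between-arm test of change.** Assume a 5.25-lesion difference between arms (the documents give none) and SD 7 in both. SE = 7 × √(1/n₁ + 1/n₂).

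- 14 vs 7: SE = 3.24; noncentrality 5.25/3.24 = 1.62; two-sided power 34%; 95% half-width 2.093 × 3.24 = 6.8 lesions.
- 20 vs 10: SE = 2.71; noncentrality 1.94; power 46%; half-width 2.048 × 2.71 = 5.6 lesions.

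**5. The existing Z-test under the same assumptions.** With no change on vehicle, the proportions with a fall are Φ(0.75) = 77% and Φ(0) = 50%. Exact two-sided power is about 30% (14 vs 7) or 34% (20 vs 10).

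**6. Extra-Poisson variation.** In a Poisson random-intercept model with between-subject SD s and fractional fall r, Var(change) = 15 + 15(1 − r) + r²s².

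- r = 0: √30 = 5.48. r = 0.3, s = 8: √(15 + 10.5 + 5.76) = 5.59. Both are below 7. If the shortfall is visit-level variation (s up to 8, r up to 0.3), the unmodified week-12 interaction contrast gave about 12-15% false positives at a nominal 5%.
- r = 0.35, s = 14: √(15 + 9.75 + 24.01) = 6.98. Here no extra variation is needed, and false positives were about 5%.

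The documents do not give s, so they do not settle which case applies.

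**The case against.** The strongest reply is that the comparison with placebo is not missing. It is pre-specified, has its own power statement, and is followed by a longitudinal model. That stands: the fault is in the ranking, not an omission. Nor does the plan say that a significant Wilcoxon result alone will be reported as superiority to placebo. It states no success rule for any test, so the absence of one cannot be held against the between-arm test in particular.

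The mixed-model wording may also be shorthand, since the authors write out the interaction for the secondary outcomes. That is possible, but the text as it stands names neither the interaction nor a contrast.

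A third reply is that exchanging the existing primary and secondary labels would be enough. That is indeed the smaller edit, and it aligns the primary test with the hypothesis. Preferring a comparison of counts is a matter of judgement; the reason for it is that the Z-test ignores the size of the change.

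A reader might also infer that the plan's SD of 7 proves overdispersion and that a Poisson contrast must be anti-conservative. Step 6 shows that this depends on the between-subject SD. The SD of 7 is also taken from a week-16 comparison in 11 UVB-treated subjects.

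**Conclusion.** The point holds as a mismatch between the primary hypothesis and the analysis labelled primary. Followed as written, the plan gives a primary result that cannot by itself support improvement compared with placebo, and a count model that does not estimate a between-arm difference in change. The mismatch follows from the text and depends on no disputed figure. Its size does depend on an assumption: the 11-59% (14 completers) and 14-76% (20 completers) rates assume equal improvement of 10-30% in both arms and normal changes with SD 7.

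The documents do not support the stronger readings that the trial lacks a placebo comparison, that the sponsor intends to claim superiority from the within-arm test, or that more subjects are needed to correct this point. It should be corrected before treatment assignments are unblinded for analysis.

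**What to change.** **Data Analysis, Primary Endpoint.** Make the Duobrii-versus-vehicle comparison of week-12 lesion counts, accounting for baseline count, the primary analysis. Either form would do:

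1. Add the time-by-treatment interaction to the count mixed model and name the week-12 between-arm contrast as primary. If the Poisson distribution is kept, allow for extra-Poisson variation as a precaution.
2. Use a baseline-adjusted comparison at week 12.

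Keep the Wilcoxon test as within-arm support and the Z-test as secondary. Exchanging the two existing labels is the minimum acceptable edit, with the loss of information noted above.

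**Sample Size Considerations.** State power for the between-arm primary test under declared assumptions, and plan to report the between-arm estimate with a 95% confidence interval.

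**Alternative.** If the within-arm test stays primary, restate the hypothesis and conclusion as within-arm and exploratory, with no claim against placebo.

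**Cost.** These are text edits using data already collected. The price is lower stated power: the 34% or 46% of step 4, against the 80% now stated for the within-arm test. Baseline adjustment may raise it, but by how much depends on the ratio of week-12 to baseline SD and on their correlation, and the documents give neither.

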## **Secondary Endpoints**

We will compare the improvement in the severity of AKN symptoms, degree of dyspigmentation, and patient-reported outcomes (DLQI and NRS) between time points (Baseline, 4, 8, and 12 Weeks) and groups (placebo and active) with the nonparametric tests described for the primary endpoint. We will also adjust, for each outcome, a generalized linear mixed-effects model including time, treatment group, their interaction as fixed effects, and a random intercept for each participant. This modeling strategy will decide each outcome's probabilistic distribution and link function based on goodness-of-fit criteria. The Spearman correlation coefficient will measure the association between reduction in lesion counts and improvement in patient-reported outcomes. In addition, we will compare the percent area of the treatment area affected with dyspigmentation (hypo- or hyperpigmentation) at each visit.

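### For lesion counts, the plan specifies no between-arm comparison of change to week 12: the one named test is an unadjusted any-reduction Z-test, and the Poisson mixed model lists no time-by-treatment interaction and names no contrast

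*Combined protocol and SAP*

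**What the plan says.** The Primary Hypothesis is comparative: it expects better lesion counts, "symptoms associated with AKN as well as minimal dyspigmentation when compared to patients receiving placebo".

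Data Analysis, Primary Endpoint, sets out three layers for lesion counts:

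- The primary analysis is a two-sided Wilcoxon test of pre- against post-treatment counts.
- The secondary analysis is the between-arm comparison at 12 weeks: "we will apply the Z-test to verify the hypothesis that the proportions of patients with reduced AKN lesions differ between active and placebo groups". No threshold for a reduction is given, so any fall counts.
- A fuller analysis is a Poisson mixed model, "including time and treatment group as fixed factors and a random intercept for each subject". It continues: "This model will include the whole time-course and contrasts of interests will be estimated". The contrasts are not named.

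Data Analysis, Secondary Endpoints, specifies the mixed models for the other outcomes as "including time, treatment group, their interaction as fixed effects". The lesion-count model does not list that interaction.

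Sample Size Considerations powers the between-arm comparison at 80% "to detect a minimum 50% difference between proportions of patients with a reduced number of AKN lesions", "based on the application of a one-sided Z-test for the difference between two independent proportions", with up to 30% dropout in each arm.

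The schedule in Appendix A marks lesion counts at baseline, weeks 4, 8 and 12, the week-14 follow-up and early termination.

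**The concern.** The hypothesis needs a between-arm comparison of lesion counts. The plan says it will compare the reduction between arms, but the test it names compares how many patients had any reduction. A fall from 15 to 14 scores the same as a fall from 15 to 0. The result gives no estimate of how far the arms differ in counts, and no section names the baseline count as a covariate.

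The Poisson model does use the counts. With main effects only, however, its treatment term is a single difference applied to every visit, including baseline, before any treatment. No contrast from such a model is a between-arm difference in change. With the contrasts also unnamed, the analysis that best addresses the hypothesis would be settled after the data are available.

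**Working it through.** **Inputs.** From the plan: 20 active and 10 vehicle, 30% dropout, baseline mean 15, a 35% reduction (0.35 x 15 = 5.25 lesions), and "a standard deviation of 7 lesions around the mean difference at week 12". Not in the plan, so assumed: the vehicle response, the count distribution and the between-subject spread.

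**1. The plan's between-arm figure.** Completers: 20 x 0.7 = 14 and 10 x 0.7 = 7. The two proportions are not stated; take 25% and 75%.

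- Standard error (unpooled) = sqrt(0.1875/14 + 0.1875/7) = 0.2004.
- 0.5 / 0.2004 = 2.494.
- One-sided power = Phi(2.494 - 1.645) = 0.802. The stated 80% reproduces.

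**2. What the literal Poisson model estimates.** The model is log E(count) = time effect + b x arm + subject intercept, with the same b at every visit. With complete data, b depends only on each subject's total over visits. Assume equal arms at baseline, a flat vehicle arm, and an active arm at 0.65 of baseline by week 12. Using baseline and weeks 4, 8 and 12:

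- Log-linear build-up: (1 + 0.866 + 0.750 + 0.650) / 4 = 0.82.
- Full effect from week 4: (1 + 3 x 0.65) / 4 = 0.74.

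The week-12 ratio of changes is 0.65 in both cases. If week 14 also enters the model and the effect holds, the averages are (3.267 + 0.65)/5 = 0.78 and (2.95 + 0.65)/5 = 0.72. The dilution remains because baseline is still averaged in.

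**3. Adding the interaction.** The week-12 contrast, (active week 12 / active baseline) / (vehicle week 12 / vehicle baseline), then recovers 0.65. Overdispersion matters. In simulation (14 vs 7, 8,000 trials), where the SD of 7 reflects extra-Poisson variation, the unscaled Poisson contrast has type I error of 12-17%. Scaled by the Pearson dispersion, it is 5.5-6.4%.

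**4. Baseline-adjusted comparison against the Z-test.** Simulated gamma-Poisson counts (assumed), baseline mean 15, between-subject log SD 0.3 or 0.5 (assumed), overdispersion tuned so that the SD of change is 7 in the vehicle or the active arm. 14 vs 7, two-sided 5%, 20,000 trials per setting (rank-sum 4,000), active counts multiplied by 0.65:

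| Method | 0.3, vehicle | 0.3, active | 0.5, vehicle | 0.5, active |
|---|---|---|---|---|
| ANCOVA, raw count | 0.559 | 0.501 | 0.498 | 0.482 |
| ANCOVA, log(count+1) | 0.504 | 0.448 | 0.435 | 0.427 |
| t-test on change | 0.381 | 0.327 | 0.357 | 0.344 |
| Rank-sum on change | 0.352 | 0.290 | 0.324 | 0.312 |
| Pooled Z, any reduction | 0.353 | 0.304 | 0.343 | 0.324 |

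Null rejection rates are about 5% for both ANCOVAs (raw 4.5-5.1%, log 4.7-5.0%) and for the pooled Z-test (4.9-5.0%).

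With an additive fall of 5.25 lesions instead, log-count ANCOVA gives 0.493/0.443/0.510/0.491 and the pooled Z-test 0.395/0.340/0.445/0.430, a gain of 6-10 points.

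**5. Using all visits.** With 20 vs 10 randomised, 6 and 3 lost at random after weeks 4 and 8, and log-linear build-up, power is 48-55% for a log-count mixed model with baseline as covariate, 45-54% for the dispersion-scaled Poisson model with interaction, and 43-50% for log-count ANCOVA in completers. These runs use no early-termination counts.

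**The case against.** The strongest reply has five parts.

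- **The Z-test is legitimate.** It is the test the trial was sized on, the sizing reproduces, and the pooled form holds its error rate near 5% in the simulations. This stands. A reader might infer that the 80% figure is wrong; at 25% against 75%, one-sided, it is not. The sizing is one-sided while the analysis asks whether proportions differ (two-sided: Phi(2.494 - 1.960) = 0.703). That is a separate point about the sample-size section.
- **Baseline is not ignored.** A patient can only be reduced relative to baseline, so a reading that the Z-test leaves baseline out is not supported. What stands is narrower: the test discards the size of the fall and does not adjust for baseline.
- **The missing interaction is probably a drafting slip.** The secondary-endpoint models list it, and the lesion-count text promises contrasts. That is plausible, and it makes the repair easy. As written, though, the listed terms cannot yield a difference in change.
- **Ending the dichotomy gains little.** This stands. A t-test on change adds 1-3 points over the pooled Z-test, and the rank-sum test adds nothing. Most of the gain comes from adjusting for baseline.
- **The form of ANCOVA is a preference, and the gains rest on assumed distributions.** This also stands. The log(count+1) form is less powerful here than raw counts. It estimates a ratio of geometric means of count+1, so a true 0.65 comes back as about 0.66-0.67. It should be one option, not a requirement.

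**Conclusion.** The concern holds as a gap in specification, and that conclusion depends on no power figure. For lesion counts, the plan names no baseline-adjusted between-arm comparison at week 12, and the Poisson model as listed does not test a between-arm difference in change.

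Its size is less certain. The dilution from 0.65 to 0.74-0.82 assumes a flat vehicle arm and the four visits from baseline to week 12. The gain from ANCOVA at 14 vs 7 (about 43-56% against 30-35%) assumes gamma-Poisson counts, an SD of change near 7 and a multiplicative 35% reduction.

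A reader might infer that better analysis rescues the comparison. It does not: power stays near one half. Nor should a power be quoted for the literal main-effects model, because the plan does not say which visits enter it. The point should be fixed. It does not invalidate the trial, and the plan itself labels this comparison secondary.

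**What to change.** 1. In Data Analysis, Primary Endpoint, add the time-by-treatment interaction to the Poisson mixed model, matching the secondary-endpoint models. Name the contrast: the between-arm difference in change from baseline to week 12. Allow for overdispersion by dispersion scaling or a negative binomial model. State whether the week-14 count, taken after study product is returned at week 12, enters the model, and how early-termination counts are assigned to visits.

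2. Make the between-arm lesion-count test a two-sided, baseline-adjusted week-12 comparison with a 95% confidence interval. It can be the contrast above or an ANCOVA of week-12 count on arm and baseline count; choose one before the data are seen. If log(count+1) is used, describe the result as a ratio of geometric means of count+1. The mixed model has the advantage of using the week-4 and week-8 counts of patients who drop out.

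3. Keep the proportion with any reduction as a descriptive or supporting result.

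**Cost.** This changes SAP wording only; every count needed is already scheduled. The between-arm test would no longer be the one the sample-size section powered, and that section should say so. The comparison remains underpowered.
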